11.1.4. Visit 4 [Day 1 to Day of Hospital Discharge (D-HD)]

On Day 1 after surgery and until the day of hospital discharge, daily assessment will be conducted and will include:

- Vital signs (blood pressure, heart rate, temperature, respiratory rate).
- Blood hematology and biochemistry (see Schedule of Assessments for the list of tests).
- Adverse events (in particular related to post-operative adhesions, systemic inflammation, bleeding / thrombotic and transfusion-related complications).
- Transfusion requirements.
- Concomitant medications.

11.1.5. Visit 5 [Day of Hospital Discharge (D-HD)]

At the time of discharge the following assessment will be conducted and recorded on the eCRF and in the study file:

- Physical examination and documentation of any changes in medical history.
- Vital signs (blood pressure, heart rate, temperature, respiratory rate).
- Blood hematology and biochemistry (see Schedule of Assessments for the list of tests).
- Measurement of coagulation parameters (PT, PTT, INR).
- Urine analysis (see Schedule of Assessment for the list of tests).
- Adverse events (in particular related to post-operative adhesions, systemic inflammation, bleeding / thrombotic and transfusion-related complications).
- Transfusion requirements.
- Concomitant medications.

11.1.6. Visit 6 (Day 30±3 after surgery) – Follow up Visit #1

The following information will be recorded at the clinical follow-up visit approximately one month following surgery:

- Physical examination and documentation of any changes in medical history.
- Vital signs (blood pressure, heart rate, temperature, respiratory rate).
- Blood hematology and biochemistry (see Schedule of Assessments for the list of tests).
- Measurement of coagulation parameters (PT, PTT, INR).
- Urine analysis (see Schedule of Assessment for the list of tests).
- Testing of antibodies levels (against Human Fibrinogen and Human Thrombin).
- Adverse events (in particular related to post-operative adhesions, systemic inflammation, bleeding / thrombotic and transfusion-related complications).
- Transfusion requirements.
- Concomitant medications.

11.1.7. Visit 7 (Day 60±7 after surgery) – Follow up Visit #2

The following information will be recorded at the clinical follow-up visit approximately one month following surgery:

- Physical examination and documentation of any changes in medical history.

- Vital signs (blood pressure, heart rate, temperature, respiratory rate).
- Blood hematology and biochemistry (see Schedule of Assessments for the list of tests).
- Adverse events (in particular related to post-operative adhesions, systemic inflammation, bleeding / thrombotic and transfusion-related complications).
- Transfusion requirements.
- Concomitant medications.

11.1.8. Visit 8 (Day 120±14 after surgery) – Follow up Visit #3

The following information will be recorded at the clinical follow-up visit approximately one month following surgery:

- Physical examination and documentation of any changes in medical history.
- Vital signs (blood pressure, heart rate, temperature, respiratory rate).
- Blood hematology and biochemistry (see Schedule of Assessments for the list of tests).
- Adverse events (in particular related to post-operative adhesions, systemic inflammation, bleeding / thrombotic and transfusion-related complications).
- Transfusion requirements.
- Concomitant medications.

11.1.9. Visit 9 (Day 180±14 after surgery) – Follow up Visit #4

The following information will be recorded at the clinical follow-up visit approximately six months following surgery:

- Physical examination and documentation of any changes in medical history.
- Vital signs (blood pressure, heart rate, temperature, respiratory rate).
- Blood hematology and biochemistry (see Schedule of Assessments for the list of tests).
- Measurement of coagulation parameters (PT, PTT, INR).
- Urine analysis (see Schedule of Assessment for the list of tests).
- Testing of antibodies levels (against Human Fibrinogen and Human Thrombin).
- MRI assessment of the intervention site (mainly to exclude post-operative adhesions). This assessment can be done earlier in patients reporting abdominal symptomatology suspect for intra-abdominal adhesions or intestinal obstruction (ref. 12).
- Adverse events (in particular related to post-operative adhesions, systemic inflammation, bleeding / thrombotic and transfusion-related complications).
- Transfusion requirements.
- Concomitant medications.

All patients can request or be requested to be evaluated in an additional visit (i.e., in case of suspected adverse events). In such case will be examined as needed indicated at Section 13.5.

11.2. Procedures for Handling of Biological Samples

All laboratory investigations will be performed at the local hospital laboratory. The volume of blood to be taken will be determined according to the standard practices of each hospital. The normal reference ranges and laboratory accreditation certificates will be provided by the local site laboratory. Testing of antibodies (against Human Fibrinogen and Human Thrombin) will be performed at a central laboratory. In case of positive results for immunogenicity, an antibody retesting using a second separately drawn sample as confirmatory measurement will be performed.

12. EFFICACY AND SAFETY ASSESSMENTS

12.1. Primary Endpoint

The primary endpoint of the study is the evaluation of safety. Safety will be assessed from randomization of patients until the last follow-up visit and will include evaluation of treatment emergent adverse events. In particular, patients will be followed for AEs related to bleeding at TBS, thrombotic events, transfusion-related complications, post-operative adhesions (MRI assessment) as well as vital signs, physical examination, urine analysis, blood / coagulation parameters profiles, antibodies against fibrinogen and thrombin, and signs of systemic inflammation. For assessment of AEs please see Section 13.

12.2. Secondary Endpoints

The secondary endpoints of the study are:

- Proportion of patients achieving hemostasis at TBS (absence of bleeding) at 2 (for sFilm-FS product only), 3, 5, 7 or 10 minutes following first product application, without the occurrence of re-bleeding, starting from 10 minutes after product application and until the completion of surgical closure.
- Incidence of re-treatment (one or more additional patch of sFilm-FS or TACHOSIL[®]) at the TBS at the different time points (2 for sFilm-FS, 3, 5, 7, 10 minutes from first product application).
- Time to Hemostasis from first product application (TTHP). Time to Hemostasis from patient randomization (TTHR) will be collected as well but will not be used as endpoint.
- Percentage of total patients (patients that achieved hemostasis with a single patch application and patients that required additional patches) that have achieved hemostasis 10 minutes after first product application and therefore did not need to convert to standard of care treatment at the end of these 10 minutes.
- Incidence of treatment failure based on pre-defined treatment failure criteria (see definition in Section 11.1.3 of the protocol).
- Incidence of transfusion requirements in the 6 months follow-up period.

13. ASSESSMENT OF ADVERSE EVENTS

Safety will be assessed in all patients participating in the clinical study including monitoring of adverse events, as specified below.

13.1. Adverse Event (AE)

An adverse event (AE) is defined as any untoward medical occurrence in a patient or clinical trial patient administered a medicinal product and which does not necessarily have a causal relationship with the treatment. In the study, any adverse event occurring after the clinical trial patient has signed the study Informed Consent should be recorded on the eCRF and reported as an AE. An adverse event can therefore be any unfavorable and unintended sign (including an abnormal laboratory finding), symptom, or disease temporally associated with the use of an investigational medicinal product, whether or not considered related to the investigational medicinal product. A new condition or the worsening of a pre-existing condition will be considered an AE. Stable chronic conditions such as arthritis that is present prior to study entry and do not worsen during

the study will not be considered AE. Medical conditions/diseases present before starting study are only considered adverse events if they worsen after starting study treatment.

Abnormal results of diagnostic procedures, including abnormal laboratory findings, will be considered an AE if it:

- it is associated with significant clinical signs or symptoms;
- requires therapy.

Post-operative adhesions will be considered adverse events in this study. A MRI assessment will be performed at Visit 1 (Screening) and at Visit 7 (6 months post-surgery) for detection of intra-abdominal adhesions, or earlier in patients reporting abdominal symptomatology suspect for intra-abdominal adhesions or intestinal obstruction (ref. 12).

Systemic inflammation will be evaluated by the investigator, based on the following assessments:

- Body temperature, heart rate, respiratory rate, white blood cell count, CRP

The intensity or severity of the AE will be characterized as:

- Mild: AE which is easily tolerated.
- Moderate: AE sufficiently discomforting to interfere with daily activity.
- Severe: AE which prevents normal daily activities.

The relationship of an AE to the study product must be assessed by the Investigators using the following criteria and definitions:

Unrelated	This category applies to those adverse events which, after careful consideration, are clearly due to extraneous causes (disease, environment, etc.)	
Unlikely	In general, this category can be considered applicable to those adverse events, which after careful medical consideration at the time they are evaluated, are judged to be unrelated to the test drug.	
An adverse experience may be considered unlikely related if or when (must have two):
 
 • It is an unknown reaction to the test drug • It does not follow a reasonable temporal sequence from the administration of the test drug. • It could have been produced by the patient's clinical state, environmental or toxic factors, or other treatments administered to the patient. 
It does not reappear or worsen when the drug is re-administered.

Possibly	
This category applies to those adverse events for which, after careful medical consideration at the time they are evaluated, a connection with the test drug administration appears unlikely but cannot be ruled out with certainty.
	
An adverse experience may be considered possibly related if or when (at least two of the following):
 
 • It follows a reasonable temporal sequence from administration of the drug. • It could not be produced by the patient's clinical state, environmental or toxic factors, or other treatments administered to the Patient. • It is a known reaction to the test drug.
Probably	
This category applies to those adverse events which, after careful medical consideration at the time they are evaluated, are felt with a high degree of certainty to be related to the test drug.
	
An adverse experience may be considered probably related if or when (at least three of the following):
 
 • It follows a reasonable temporal sequence from administration of the drug. • It could not be reasonably explained by the known characteristics of the patient's clinical state, environmental or toxic factors or other modes of therapy administered to the patient. • It disappears or decreases after discontinuation (de-challenge) of test drug or reduction of posology • It is a known reaction to the test drug.
Definitely	
This category applies to those adverse events which, after careful medical consideration at the time they are evaluated, are considered to be related to the test drug.
	
An adverse experience may be considered certainly related if or when:
 
 • it follows a reasonable temporal sequence from administration to the clinical event - including laboratory test abnormalities - • which cannot be explained by a concomitant illness or by other medicinal products. • The reaction must have already been observed for the suspected medicinal product. • The reaction must improve with "de-challenge" and reappear with "re-challenge".

The date of onset, a description of the AE, severity, seriousness, action taken, relationship to the study drug, outcome of the event and date of resolution will be recorded.

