7.3.2. Stopping Rules

If one of the following occurs during the enrollment period of patients receiving the test article (sFilm-FS) the study will be immediately suspended:

- Three or more patients developed a suspected unexpected serious adverse reaction (SUSAR) caused by a TBS post-operative re-bleeding (not requiring surgery re-intervention);
- Two or more patients had a TBS re-bleeding events following final observation period that required surgery re-intervention;
- Three or more patients developed other possible serious adverse reactions like thromboembolic events or severe allergic reactions.
- Three or more patients develop serious unanticipated or unexpected local reactions (serious adverse events) such as:
 - Signs of local reactions affecting the spleen and liver (persistent pain in the area of the application that is unanticipated or unexpected)
 - Persistent unanticipated and unexpected Systemic inflammatory response syndrome (SIRS), defined with at least two of these conditions: body temperature over 38 or under 36 degrees Celsius, heart rate greater than 90 beats/minute or respiratory rate greater than 20 breaths/minute or partial pressure of CO₂ less than

- 32 mmHg, leucocyte count greater than 12000 or less than 4000 /microliters or over 10% immature forms or bands
- Reactions on other local organs such as adhesions and reactions impacting the intestinal tract etc., assessed as being due to local reactivity. This would be diagnosed as a bowel obstruction that is unanticipated.

These stopping rules only apply to the investigational treatment group (Group A). The active-comparator group (Group B) patients should be followed according to the Investigator's standard practice as clinically appropriate.

After study suspension, the Data Safety Monitoring Board (DSMB), together with the Sponsor, will review the data and decide whether to continue or terminate the study.

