An "Unexpected Adverse Drug Reaction" is any noxious and unintended response that is related to the administration of an investigational product that has not been reported as expected in the Summary of Product's Characteristics or in the Investigator's Brochure.

All SUSARs related to the investigational product will be subject to expedite reporting.

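### The causality criteria in Protocol 13.1 count novelty towards 'Unlikely', so by count a well-timed event with another possible cause is 'Unlikely' if new and 'Possibly' if known, although the definition of 'Possibly' fits both

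*Protocol*

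**What the plan says.** Protocol 13.1 is directive about the method: "The relationship of an AE to the study product must be assessed by the Investigators using the following criteria and definitions". Each grade then has a verbal definition and, apart from *Unrelated*, a list of criteria.

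- ***Unlikely***: events that "are judged to be unrelated to the test drug". Two criteria must hold. The bulleted ones are "It is an unknown reaction to the test drug", implausible timing, and the possibility of another cause. A fourth line, printed without a bullet, concerns no recurrence on re-administration.
- ***Possibly***: a connection that "appears unlikely but cannot be ruled out with certainty". At least two of three must hold: plausible timing, no other possible cause, and "It is a known reaction to the test drug".
- ***Probably***: at least three of four. The list is close to that for *Possibly*, with improvement on de-challenge added.
- ***Definitely***: among other things, "The reaction must have already been observed for the suspected medicinal product".

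The grade is used elsewhere. Protocol 13.3 builds the SUSAR on a response "related to the administration of an investigational product that has not been reported as expected". One suspension rule in Protocol 7.3.2 reads "Three or more patients developed a suspected unexpected serious adverse reaction (SUSAR) caused by a TBS post-operative re-bleeding". Protocol 14.8.3 and SAP 6.12.2 tabulate related events. Protocol 13.2 glosses related as possibly or probably.

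SAP 6.12.2 uses a different five-step scale taken from the CRF (none, unlikely, possible, probable, highly probable). It neither maps this to the protocol's scale (unrelated to definitely) nor says which steps count as IMP-related.

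**The concern.** Whether a reaction has been seen before bears on expectedness. Here it also decides causality, and it works against the new reaction. The two lists are mirror images on novelty, so two events with the same timing and the same competing explanation can fall on opposite sides of the related/unrelated line. The definitions do not mention novelty at all, so criteria and definitions that must be used together give different answers.

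Safety is the primary endpoint, and the Protocol's Introduction presents sFilm-FS as new. A SUSAR has to be both related and not already listed as expected. The scale therefore lowers the causality grade of the kind of event that could become one. Because every treated patient has had surgery with liver bleeding, a competing explanation will often be arguable.

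**Working it through.** The plan gives no figure to reproduce. The check is a count over the printed criteria.

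**Inputs** (Protocol 13.1), each 0 or 1: T = timing plausible; A = another cause possible; K = reaction known; D = improvement on de-challenge credited; R = the unbulleted re-administration line credited.

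**Scores**
- Unlikely: U = (1−K) + (1−T) + A + R, threshold 2
- Possibly: P = T + (1−A) + K, threshold 2
- Probably: Pr = T + (1−A) + K + D, threshold 3

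**Base case**: R = 0 and D = 0. This suits a patch that is left in place once adherent (Protocol 11.1.3). The highest grade met is kept.

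| T | A | Known: U / P, grade | New: U / P, grade |
|---|---|---|---|
| 1 | 1 | 1 / 2, Possibly | 2 / 1, Unlikely |
| 1 | 0 | 0 / 3, Probably (Pr = 3) | 1 / 2, Possibly |
| 0 | 1 | 2 / 1, Unlikely | 3 / 0, Unlikely |
| 0 | 0 | 1 / 2, Possibly | 2 / 1, Unlikely |

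Changing known to new crosses from *Possibly* to *Unlikely* in 2 of the 4 combinations. It lowers *Probably* to *Possibly* in 1 (still related under Protocol 13.2) and changes nothing in 1. These are outcomes of the rule, not frequencies of events.

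**Sensitivity, first row (T = 1, A = 1)**

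| R | D | Known: U / P / Pr | New: U / P / Pr |
|---|---|---|---|
| 0 | 0 | 1 / 2 / 2 | 2 / 1 / 1 |
| 1 | 0 | 2 / 2 / 2 | 3 / 1 / 1 |
| 0 | 1 | 1 / 2 / 3 | 2 / 1 / 2 |
| 1 | 1 | 2 / 2 / 3 | 3 / 1 / 2 |

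With R credited, the known event meets both *Unlikely* and *Possibly*. The new event meets *Unlikely* in all four variants and never *Possibly* or *Probably*.

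**Definitions against the same row.** If timing is plausible and another cause is only possible, a connection has not been excluded. That is the definition of *Possibly*, whatever K is. An event whose connection remains open has not been judged unrelated, so the definition of *Unlikely* does not fit.

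**Would deleting the novelty item be enough?** The new event in the first row would then score U = 0 + 1 = 1 and P = 1, so it reaches neither threshold. The same holds for T = 0, A = 0 (U = 1, P = 1). With R credited, the first-row event still scores U = 2 against P = 1. Deletion alone therefore does not settle the grade; a rule on which text governs is also needed.

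**The case against.** The best reply is that the lists are permissive. They say an event *may* be so considered, the *Unlikely* definition opens with a general qualifier, and both call for careful medical judgement. An investigator who cannot exclude a connection may simply follow the definition. That stands, and it means the counts do not force the wrong grade. It does not remove the conflict: two investigators can grade the same event differently and both comply.

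The clean split also depends on how the unbulleted line is read, since crediting it puts the known event in both grades. That stands for the known event only.

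Third, the effect in practice cannot be seen from these documents. What is known rests on product information they do not reproduce, and the SAP reports a CRF scale that differs from the protocol's. That stands too, and it rules out any estimate of size.

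Several stronger readings are tempting and not supported:

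- *A new reaction cannot be rated related, or cannot become a SUSAR.* A well-timed new event with no other explanation scores 2 for *Possibly*. Moreover, *known* in 13.1 is not defined as *expected* in 13.3.
- *The rule favours sFilm-FS over TACHOSIL by some amount.* Known reactions are listed for neither product, and the fibrinogen and thrombin in sFilm-FS are themselves licensed components (Protocol 5.1).
- *A low grade ends follow-up.* Protocol 13.5 asks for follow-up of all AEs.
- *Late SAEs graded Unlikely go unreported.* Protocol 13.2 and 13.5 also trigger on relation to study participation, so that route is only partly affected.
- *The DSMB would not see such events.* Protocol 7.4 sends it all AE reports.

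**Conclusion.** The point holds as a conflict between criteria and definitions that works against new reactions. By the printed counts, a well-timed event with another possible cause is *Unlikely* if new (2 against 1) and *Possibly* if known (1 against 2), although the definition of *Possibly* covers both. The result for the new event does not depend on how the re-administration and de-challenge items are scored. The result for the known event assumes that the re-administration line is not credited or that the higher grade is kept.

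Where investigators follow the counts, related-AE tables can be too low. SUSAR status, and with it the re-bleeding suspension rule that counts SUSARs, becomes harder to reach for new sFilm-FS reactions. Whether the separate suspension rule on other possible serious adverse reactions is touched depends on how that term is read. The number of events concerned, and any difference between arms, is unknown.

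The tables of all TEAEs, thrombotic events, TBS bleeding and MRI findings (SAP 6.12.2 to 6.12.4) are not affected, nor is in-study SAE reporting (Protocol 13.4). The primary safety assessment therefore does not fall with this point, but its causality-based part needs repair. The missing scale mapping in SAP 6.12.2 needs correcting whatever is decided about 13.1.

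**What to change.** **Protocol 13.1.** Delete the unknown-reaction item from the *Unlikely* list. State that where count and definition disagree, or no count is reached, the definition governs. An event whose connection cannot be excluded is then at least *Possibly*, and *Unrelated* remains for events clearly due to extraneous causes. Use listed or unlisted status for expectedness under 13.3 instead. Reconcile 7.3.2, 13.1 and 13.3 so that causality and expectedness are kept apart.

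**SAP 6.12.2.** Map the protocol scale to the CRF scale, and define IMP-related as possible or higher, in line with Protocol 13.2.

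**If ratings are already recorded.** Base the between-arm safety comparison mainly on the tables that ignore causality. Use the relationship breakdown already planned in SAP 6.12.2 to show the events graded unlikely.

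**Cost.** With ratings already recorded: one mapping and one definition in the SAP, and no new table. With rating still under way: also a short protocol and CRF amendment. The downside is that more AEs will be rated as related in both arms.

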Study Procedure	
The surgical procedure will be performed as per standard of care at the investigational site. A target bleeding site (TBS) will be identified intra-operatively by the Investigator when liver bleeding is encountered during surgery and conventional methods of bleeding control are ineffective.
 
Target Bleeding Site (TBS) is defined as the first bleeding site in which conventional methods of bleeding control (i.e., suture, ligature, cautery) are ineffective or impractical. The TBS must be a site where occlusion of the injured surface blood vessels is required to achieve hemostasis. It must be possible to cover the TBS adequately, with an appropriate overlap, using a single unit of product (sFilm-FS or TACHOSIL[®]). This excludes bleeding from large defects in large arteries or veins requiring repair.
 
Once the TBS has been identified, the Investigator will immediately enroll and randomize the patient into one of the following treatment arms, according to a pre-determined randomization scheme:

	
 • Group A (investigational product): sFilm-FS will be applied at the target bleeding site immediately after conventional methods of control have been exhausted. The sFilm-FS should cover adequately the entire TBS. Following application of sFilm-FS, the Investigator will immediately apply manual compression continuously for at least 2 minutes. A surgical sponge may be used to assist in providing adequate pressure. Hemostasis will be assessed after carefully releasing the compression at the site. sFilm-FS should not be removed once bleeding has stopped. A maximum of 4 units of sFilm-FS may be used per patient. • Group B (active comparator): TACHOSIL® will be applied at the target bleeding site immediately after conventional methods of control have been exhausted. TACHOSIL® should be applied as per the approved prescribing information, with manual compression for at least 3 minutes. A maximum of 4 units of TACHOSIL® may be used per patient. 
If additional bleeding sites/regions requiring a topical hemostatic product are identified after the treatment of the initial target bleeding site, these bleeding sites should be treated with the same study treatment according to the patient's randomization assignment, if clinically appropriate. These areas will not be assessed for hemostasis, but information will be recorded.

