6.12.2 Adverse events and Serious Adverse events

All AE will be coded according to MeDDRA version 25.1.

Concerning Adverse Events (AE) a summary of treatment-emergent adverse events (TEAE), including the total number of events reported, the number and percentage of patients reporting at least one adverse event, the number and percentage of IMP-related adverse events, the number and percentage of patients withdrawing prematurely due to an adverse event, the number and percentage of patients with at least one serious adverse event (SAE), the number of non-fatal serious adverse events and the number and percentage of deaths, will be presented by treatment.

A further tabulation of TEAEs by SOC and PT, and TEAEs by SOC and PT broken down by relationship to study drug will be presented. Relationship to study drug is categorized as none, unlikely, possible, probable and highly probable as recorded on the CRF. A summary of TEAEs reported by SOC and PT, broken down by severity (mild, moderate, severe, life threatening), will also be provided. In addition IMP related adverse events, deaths and non-fatal serious adverse events will be tabulated.

A summary of TEAEs leading to premature withdrawal will be provided, grouped by body

	STATISTICAL ANALYSIS PLAN	FSTAT.01.03
Study Code: HEM-HEM-01-17		Sealantium Medical Ltd.

system and preferred term.

All tabulations by SOC and PT will be replicated for all serious TEAEs.

All adverse events recorded on the CRF will be listed.

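### AE causality criteria rely on de-challenge and re-challenge, which a patch left in place cannot provide: *Definitely* is unattainable, *Probably* needs a known reaction, and the SAP scale is not mapped to the protocol's

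*Protocol*

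**What the plan says.** Protocol 13.1 says investigators must assess relationship with the listed criteria. There are five grades, and the upper four carry lists:

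- *Unlikely* needs two items: reaction not known, timing not plausible, another cause possible. A further line stands under the same heading: "It does not reappear or worsen when the drug is re-administered".
- *Possibly* needs at least two of three: plausible timing, no other cause, known reaction.
- *Probably* needs at least three of four: the same three plus "It disappears or decreases after discontinuation (de-challenge) of test drug or reduction of posology".
- *Definitely* lists plausible timing and no explanation from illness or other medicines. It adds "The reaction must have already been observed for the suspected medicinal product" and a last mandatory line: "The reaction must improve with 'de-challenge' and reappear with 're-challenge".

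On use of the product, the protocol synopsis states "sFilm-FS should not be removed once bleeding has stopped". Protocol 11.1.3 has either product applied on Day 0 and left in place once it adheres. The only removal it describes is of a patch that failed to adhere, during the operation. No later administration is planned.

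For reporting, SAP 6.12.2 states: "Relationship to study drug is categorized as none, unlikely, possible, probable and highly probable as recorded on the CRF". Protocol 14.8.3 and SAP 6.12.2 both tabulate related events, but neither says which grades count as related. Protocol 13.2, on serious events after the study period, treats possibly and probably as related.

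**The concern.** Two of the four graded categories depend on stopping the product, and the top one also depends on giving it again. In this trial neither happens after the operation. The line about re-administration under *Unlikely* cannot be tested either, and nothing says whether an untestable line counts as met, as not met, or not at all.

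Safety is the primary endpoint, and the SAP breaks down treatment-emergent events by relationship within system organ class and preferred term. The judgement also bears on which events qualify as SUSARs (Protocol 13.3) and on those stopping rules in 7.3.2 that count suspected or possible reactions to sFilm-FS. For a new implant the most informative event is a reaction nobody has listed yet, and the criteria handle that kind of event worst.

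**Working it through.** The documents give no figure on this point, so the check applies the printed counting rules to every possible profile.

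**Inputs (Protocol 13.1).** Three facts can be assessed for any event: timing plausible (yes/no), no other explanation (yes/no), known reaction (yes/no). That gives 2 × 2 × 2 = 8 profiles. The small differences in how each grade words the absence of another cause are treated as one fact.

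Let *s* be the number of these three facts that point to the product. The profiles with *s* = 0, 1, 2, 3 number 1, 3, 3, 1. Let *d* = 1 if a positive de-challenge exists and *r* = 1 if the re-administration line under *Unlikely* is counted as met.

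**Rules as formulas.**

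- *Possibly*: *s* ≥ 2
- *Probably*: *s* + *d* ≥ 3
- *Definitely*: *s* = 3, plus positive de-challenge and re-challenge
- *Unlikely*: (3 − *s*) + *r* ≥ 2

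**Results.**

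| Grade | Condition | Profiles qualifying |
|---|---|---|
| *Definitely*, de- and re-challenge positive | *s* = 3 | 1 of 8 |
| *Definitely*, this trial | cannot be met | 0 of 8 |
| *Probably*, de-challenge positive (*d* = 1) | *s* ≥ 2 | 3 + 1 = 4 of 8 |
| *Probably*, this trial (*d* = 0) | *s* = 3 | 1 of 8 |
| *Possibly* | *s* ≥ 2 | 3 + 1 = 4 of 8 |
| *Unlikely*, line not counted (*r* = 0) | *s* ≤ 1 | 1 + 3 = 4 of 8 |
| *Unlikely*, line counted (*r* = 1) | *s* ≤ 2 | 1 + 3 + 3 = 7 of 8 |
| Both *Unlikely* and *Possibly*, *r* = 0 | *s* ≤ 1 and *s* ≥ 2 | 0 of 8 |
| Both *Unlikely* and *Possibly*, *r* = 1 | *s* = 2 | 3 of 8 |

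**The new reaction.** Plausible timing, no other explanation, not known: *s* = 2. It meets 2 of the 3 items needed for *Probably*, so its ceiling is *Possibly*. With *r* = 1 it also qualifies as *Unlikely*.

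**Scales side by side.** The protocol runs Unrelated, Unlikely, Possibly, Probably, Definitely. The SAP runs none, unlikely, possible, probable, highly probable. The first four correspond in order. The fifth does not share a name, and neither document gives criteria for highly probable or maps it to *Definitely*.

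The fractions count logical profiles. They are not expected shares of events, because the profiles will not be equally common.

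**The case against.** The strongest reply is that the consequences are small. A reader might infer that product-related harm is under-reported by rule. The documents do not support that. Events that lose *Definitely* or *Probably* fall to *Possibly*, which Protocol 13.2 treats as related, and one stopping rule in 7.3.2 is worded in terms of possible reactions. No cut-off above *Possibly* is stated, so no count of related events is shown to change.

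Much of the safety reporting does not use the grade at all. All adverse events and serious adverse events are tabulated, serious events are reported whatever their cause (13.4), the DSMB receives the adverse event reports (7.4), and the stopping rule on re-bleeding that needs re-intervention uses no grade. This stands, and it limits the point to the tables by relationship grade.

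A reader might also infer that the untestable line pushes events into *Unlikely*. That holds only if the line is counted as met, which the protocol does not say; it may equally be read as not applicable. In the text available the line also sits outside the bulleted items, which may be an effect of extraction. And of the four profiles with another explanation, three already reach two *Unlikely* items without it. An unlisted event that the operation could explain is *Unlikely* either way, so removing the line would not alter that result.

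Three further replies carry less weight:

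- The lists say an event may be considered to have a grade, which leaves room for judgement. But 13.1 makes use of the criteria mandatory.
- A non-adherent patch can be removed and patches added during surgery. That could bear only on immediate intra-operative reactions.
- The rules are the same in both arms, so no clear bias between arms follows. The known-reaction item is probably easier to meet for the licensed comparator, but the documents do not allow that to be sized.

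The eCRF is not among the documents and may carry its own grading instructions.

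**Conclusion.** The point holds for the grading itself. For a patch applied in one operation and left in place, *Definitely* is unattainable in both arms (0 of 8 profiles). *Probably* shrinks from 4 of 8 profiles to 1 of 8, the one that includes a known reaction. A new, well-timed, otherwise unexplained reaction to sFilm-FS stops at *Possibly*. The treatment of the re-administration line is unspecified, and the two readings give an overlap between *Unlikely* and *Possibly* of 3 of 8 or none. The SAP's top grade is unmapped and its related category has no stated cut-off.

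The effect is a distortion of the tables by relationship grade. A lower count of related events remains a risk: it would arise if a cut-off above *Possibly* were used, or if the re-administration line were counted as met and an overlapping event were then graded *Unlikely*. The conclusion assumes that the criteria are applied as printed, that resorption of the patch is not a discontinuation, and that the eCRF does not already override the protocol's wording.

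**What to change.** 1. In Protocol 13.1 and the eCRF guidance, strike the de-challenge, re-challenge and re-administration items, or state that they are not applicable and never count as met.
2. Reset the thresholds for *Probably* and *Definitely* on items that can be observed, such as timing and absence of another reasonable explanation. Striking the de-challenge item alone is not enough: three of the remaining three would still be required. The prior-observation requirement under *Definitely* needs the same review, because on its own it shuts out a new reaction.
3. Do not make evidence at the application site a condition for any grade. That would again close the top grade to systemic reactions such as thromboembolic or allergic events, which 7.3.2 names.
4. Use one set of grade names in the protocol, eCRF and SAP 6.12.2.
5. Define IMP-related in the SAP as possibly or higher, in line with Protocol 13.2.

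The cost is wording in three documents and, for events already entered, a supplementary re-grading. With 30 completing patients planned, this can be done at the medical review of safety data that SAP 6.12 already schedules before database lock. Because the trial is open-label, re-grading with treatment known could introduce bias. The investigators' entered grades should therefore be kept and reported beside the supplementary ones.
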